11.2.2. POPULATION DESCRIPTION

The following analyses will be performed:

- A flow chart depicting the number of patients available in the database satisfying each cohort criteria;
- A description of baseline characteristics for each cohort;
- A comparison of baseline characteristics between the PUL cohort and the TURP cohort with mean standardized differences (significant difference at the threshold of 10%) and p-value (significant difference at the threshold of 0.05);
- A comparison of baseline characteristics between the PUL cohort and the SDNS cohort according to the treatment group with mean standardized differences (significant difference at the threshold of 10%) before and after hDRS matching;
- The hDRS will be estimated using a multivariable logistic regression model including a large set of variables collected within the one year preceding surgical procedure.

¹ Glick HA. Sample size and power for cost-effectiveness analysis. 2011;29(3):189/98, Pharmacoeconomics, 2011

11.2.3. COST-EFFECTIVENESS CRITERIA

We will assess the cost-effectiveness ratio as following: $\Delta C/\Delta E = (Ceval - Cref)/(Eeval-Eref)$ where

- $\Delta C = \cos t$ differences between both surgery
- ΔE = effectiveness differences between both surgery
- Ceval = Cost of PUL surgery
- Cref = Cost of classical surgery (TURP/laser)
- Eeval = Complications observed at 4 months in the PUL group
- Eref = Complications observed at 4 months in the TURP/laser group

The ratio assessment for the second economic criteria (incremental cost/Qalys at 12 months) is the same.

First an unadjusted estimate of the cost-effectiveness ratios will be made. Their 95% confidence interval of the ratio will be estimated by bootstrap. We will then estimate the net monetary benefit of each surgical procedure (BNM = E λ - C), where λ is the differential cost - effectiveness threshold. The distribution of each BNM will be determined by boostrap. This will allow us to develop an acceptability frontier, a curve representing the probability that the BNM of each surgical treatment will be highest for each value of λ between $0 \in$ and $30000 \in$ per avoided complication (or Qaly in the secondary criteria).

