3. STUDY OUTCOMES

3.1. PRIMARY OUTCOME

The primary endpoint will be the incremental cost per avoided complication (based on Clavien Dindo classification) of PUL compared to transurethral surgery 4 months after the surgical procedure.

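### Section 11.2.3 counts observed complications as effectiveness, so the primary ratio gets the wrong sign and the net-benefit ranking reverses above λ = |ΔC/ΔE| if programmed as written

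*Protocol*

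**What the plan says.** Section 3.1 of the protocol fixes the endpoint: "The primary endpoint will be the incremental cost per avoided complication", comparing PUL with transurethral surgery at 4 months.

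Section 11.2.3 turns this into formulas. The ratio is ΔC/ΔE, written as "Ceval - Cref)/(Eeval-Eref" (outer brackets omitted), with these definitions:

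- "ΔE = effectiveness differences between both surgery"
- "Eeval = Complications observed at 4 months in the PUL group"
- "Eref = Complications observed at 4 months in the TURP/laser group"

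The same symbol E then enters the "net monetary benefit of each surgical procedure (BNM = E λ - C" (closing bracket omitted). The bootstrap distribution of this quantity yields the acceptability curve for λ from €0 to €30,000, in euro per avoided complication or per QALY. On the secondary economic criterion the section says: "The ratio assessment for the second economic criteria (incremental cost/Qalys at 12 months) is the same".

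**The concern.** Effectiveness should rise as outcomes improve. Here E is a count or rate of harms, called effectiveness and entered with a plus sign. This conflicts with the endpoint in section 3.1 and with the unit of λ in section 11.2.3 itself. It also makes one signed formula serve two outcomes that run in opposite directions: more QALYs are better, more complications are worse.

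Sections 1.4 and 1.5 expect fewer complications with PUL, which is the situation in which the sign matters for the study's hypothesis. The results are meant to support a reimbursement file (section 1.1.2.3), so a primary ratio in the wrong quadrant, or an acceptability curve that credits complications, would be a serious error.

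**Working it through.** **Inputs from the protocol.** The two formulas and definitions of E, and λ from 0 to 30,000 (section 11.2.3); 80 patients per cohort (section 11.1); complications of Clavien-Dindo grade 2 or higher in 20–40% of patients after reference surgery (section 1.1.2.1); about 4 implants at about €500, i.e. 4 × 500 = €2,000 before any offsets (section 1.1.2.3).

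**Assumed, because the protocol does not give them.** The PUL complication rate, the net cost difference ΔC = C(PUL) − C(TURP/laser), and the cost SD. The protocol states no expected ratio or net benefit, so there is no figure of its own to reproduce.

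**Step 1, algebra.** Let d = complications avoided by PUL = E(TURP/laser) − E(PUL).

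- Ratio as written: ΔC/(−d). Per avoided complication: ΔC/d. Same magnitude, opposite sign.
- Incremental BNM (PUL minus TURP/laser) as written: −λd − ΔC. Per avoided complication: +λd − ΔC.
- The product of the two increments is ΔC² − λ²d². It is negative, meaning the two versions rank the procedures differently, exactly when λ > |ΔC/d|. Below that value they rank alike; at λ = 0 they are identical.

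This step needs no assumed number.

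**Step 2, illustration.** Assume 15% (PUL) and 30% (TURP/laser), so d = 0.15. Each cell shows as written / per avoided complication, in euro.

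| ΔC | Ratio | Incremental BNM, λ = 10,000 | Incremental BNM, λ = 30,000 | Ranking reverses above λ = |
|---|---|---|---|---|
| 0 | 0 / 0 | −1,500 / +1,500 | −4,500 / +4,500 | 0 |
| +500 | −3,333 / +3,333 | −2,000 / +1,000 | −5,000 / +4,000 | 3,333 |
| +2,000 | −13,333 / +13,333 | −3,500 / −500 | −6,500 / +2,500 | 13,333 |
| −500 | +3,333 / −3,333 | −1,000 / +2,000 | −4,000 / +5,000 | 3,333 |

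For example, with ΔC = 2,000 and λ = 30,000: as written, 30,000 × (0.15 − 0.30) − 2,000 = −6,500; per avoided complication, 30,000 × (0.30 − 0.15) − 2,000 = +2,500.

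**Step 3, reading the quadrants as written.** With ΔC = +2,000, cost is up and the so-called effectiveness is down, so PUL reads as dominated; it is in fact a trade-off at €13,333 per complication avoided. With ΔC = −500, cost and so-called effectiveness are both down, so PUL reads as a trade-off; it is in fact dominant.

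**Step 4, acceptability curve.** Assume 15% v 30%, equal mean cost, cost SD €2,000, 80 per arm, and cost independent of complications. The variance of incremental BNM is λ²(0.15 × 0.85 + 0.30 × 0.70)/80 + 2 × 2,000²/80. At λ = 5,000 this is 105,469 + 100,000, so SE ≈ 453 and z = −750/453 ≈ −1.65. The probability that PUL has the higher BNM is then:

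| λ | As written | Per avoided complication |
|---|---|---|
| 5,000 | 0.05 | 0.95 |
| 10,000 | 0.02 | 0.98 |
| 30,000 | 0.01 | 0.99 |

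**Step 5, range.** Take 20–40% for TURP/laser, 5–15% for PUL, and ΔC of −500, +500, +1,000 or +2,000. The reversal point lies between €1,429 and €20,000 in every combination but one. The exception is 20% v 15% with ΔC = 2,000, where it is 2,000/0.05 = €40,000, outside the planned range.

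**The case against.** The intent is clear elsewhere. Section 3.1 names avoided complications, section 11.2.3 calls ΔE an effectiveness difference, and λ is priced per avoided complication. The definition of E may be a careless label for the input data. An analysis plan must still be validated (sections 11.2.1 and 11.2.4) and an economist sits on the steering committee (section 12.1.1), so the slip may well be caught. All of this is fair, and it makes the consequence conditional on literal programming. It does not remove the error. The protocol states the formula and every symbol itself, so a plan that follows it inherits the wrong sign, and a plan that corrects it silently departs from the protocol on the primary endpoint.

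A reader might infer that the formulas invert the primary conclusion outright. The text does not support that: the ratio's magnitude is right, and the net-benefit ranking changes only above |ΔC/ΔE|. Equal mean cost is the case in which the reversal is widest. With ΔC = €2,000 and 15% v 30%, the two versions rank the procedures alike over 13,333/30,000 = 44% of the λ range.

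A reader might also take the negative ratio for a costlier PUL with fewer complications to mean that PUL dominates. Under the written definitions it means that PUL is dominated.

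**Conclusion.** The definition is wrong as written and should be corrected before the primary analysis. The sign error follows from the text alone and depends on no assumed rate or cost. If the formulas are followed literally, the ratio has the wrong sign and quadrant, and the net-benefit and acceptability ranking reverses for every λ above |ΔC/ΔE|. How much of the €0–30,000 range this covers depends on assumptions: all λ > 0 with equal costs, and above about €13,333 with a €2,000 cost difference and 15% v 30% complications. In one of the combinations examined the expected ranking does not reverse within the range at all. The documents do not show that the sponsor means to credit complications, nor that the reported conclusion is bound to be inverted.

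**What to change.** In section 11.2.3, for the primary criterion, define effectiveness as complications avoided: ΔE = Eref − Eeval and BNM = −λ × complications − C.

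Write the QALY version separately: ΔE = QALY(PUL) − QALY(TURP/laser) and BNM = λ × QALY − C. Add a sentence on how each quadrant of the cost-effectiveness plane is read.

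The correction should only reverse the sign. It should keep the complication measure that the protocol intends, whether patients with a complication or complication events. Replacing it with the proportion of patients free of complications could change the endpoint, because section 11.2.4 describes complications by number and type and a patient may have several.

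The cost is a change to one paragraph of the protocol, carried into the analysis plan. No data collection, sample size or patient procedure is affected.

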1.3. JUSTIFICATION OF THE METHODOLOGICAL CHOICES

A two-phases economic evaluation

Randomized controlled trials were yet conducted and the remaining question is the cost effectiveness of PUL compared to other transurethral procedure in French daily practice. That's the reason why, we decided to propose an economic evaluation as the primary objective of this study.

In order to provide all pertinent clinical and economical information comparing PUL and TURP/laser surgery over a long-term follow-up period in the French context, we propose to conduct a study in two phases.

1-In the first phase we will prospectively compare a cohort of patients treated with PUL to another cohort of patients treated with TURP/laser during one year follow-up. This part of the study will enable us to gather real-life unknown information on the use of Urolift in French hospitals daily practice and organisation (number of implants needed, length and cost of surgery, length of hospital stay...) and to collect quality of life and clinical data from French population.

2- As some consequences of the surgery, as well as differences between healthcare consumptions, can occur even after 4 months and 1 year, and because it is difficult to pursue the clinical trial over 1 year without too many lost for follow-up patients, we decided to work on health databases for the second part of this study. This second phase will cover a 3-years follow-up by analysing healthcare resources utilization in each cohort using the French nationwide claims database, the SNDS. The comparison between PUL and TURP/Laser procedures will be strengthened by a complementary analysis performed between the PUL cohort and a matched cohort of patients identified in the SNDS database with the same baseline characteristics but treated with transurethral procedures. The matching process (based on a hdDRS) and the statistical methods of adjustment will overcome the absence of randomization in the initial process of patients' assignment to the PUL or TURP cohort.

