4. STUDY DESIGN AND METHODOLOGY OF ECONOMIC EVALUATION

4.1. STUDY DESIGN

ECOLIFT is a multicenter cohort study conducted on 3 cohorts as follows:

- The PUL cohort: a sample of surgeons from the 7 investigational centers will prospectively include 80 patients with a PUL surgery in first line treatment for BOO with a 1-year follow-up. Clinical data will be enhanced with healthcare consumptions and hospitalizations from SNDS with 2-year history before BPH surgery and a follow-up of 3 years.
- The TURP/laser cohort: a sample of surgeons from the 7 investigational centers different from those who will perform the PUL procedure (if not possible, it can be exceptionally the same surgeon) will prospectively include 80 patients with a TURP or laser (HLE or GLV) surgery in first line treatment for BOO with a 1-year follow-up. Clinical data will be enhanced with healthcare consumptions and hospitalizations from SNDS with 2-year history before BPH surgery and a follow-up of 3 years.
- The SNDS cohort: will include patients from the SNDS with any transurethral surgery (TURP, HLE or GLV) in first line treatment for BOO randomly matched to patients of the PUL cohort; For each transurethral surgery (TURP, HLE or GLV), 5 patients will be matched to 1 PUL patient using a high dimensional disease risk score (hDRS) based on the one-year SNDS information before transurethral procedure. The Disease Risk Score (DRS) estimates the probability of complications occurrence in the absence of the surgery of interest (PUL). DRS will be computed from a multivariable logistic regression model using a large set of variables collected during the one-year period among the SNDS cohort.

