11.2. STATISTICAL METHODS EMPLOYED

11.2.1. GENERALITIES

Statistical analysis will be performed using SAS® software (SAS Institute, latest current version, North Carolina, USA). Qualitative and ordinal variables will be summarized by frequencies and proportions of each modality, taking into account missingness as a modality. Continuous variables will be summarized by size, number of patients with missing data, arithmetic mean, standard deviation, median, interquartile ranges and extreme values. Confidence intervals will be estimated using Normal approximation for quantitative and qualitative relevant parameters, or bootstrapping method for costs when count < 100 patients.

Standardized mean differences (*Rosenbaum*, *Rubin*, 1985) will be estimated to measure the effect size of quantitative and qualitative baseline characteristics between groups (PUL and TURP cohorts, matched patients of PUL and SNDS cohorts).

For confidence intervals, 2-sided confidence level of 95% will be used. For all tests, a 2-sided significance level of 5% will be used:

- Proportions will be compared between two independent groups using Pearson's Chi-2 test (or Fisher's exact test when expected counts are < 5)
- Means will be compared between two independent groups using Student's t-test when normal distribution is followed (or Mann-Whitney's test when normal distribution is not followed)
- Occurrence of events (retreatment, urinary symptoms) will be estimated across time using Kaplan-Meier estimator and compared between groups with logrank test.
- Adjusted comparisons between PUL and the TURP/Laser cohorts and between PUL and SNDS cohorts will be
 performed in intention-to-treat analysis using linear regression model when it involves quantitative variables,
 and using logistic regression model adjusted on potential confounders when it involves qualitative variables.

[figure not shown]
A Statistical Analysis Plan (SAP) will be developed and will be validated before the analyses.

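### The primary 4-month cost-effectiveness ratio is specified only as an unadjusted estimate between non-randomised cohorts, and no adjustment is stated for the net-benefit analysis

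*Protocol*

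**What the plan says.** Section 3.1 defines the primary result: "The primary endpoint will be the incremental cost per avoided complication (based on Clavien Dindo classification) of PUL compared to transurethral surgery 4 months" after surgery. Section 4.2 places this comparison between the PUL and TURP/laser cohorts. Section 4.1 describes a cohort study without random allocation, in which the TURP/laser surgeons are "different from those who will perform the PUL procedure (if not possible, it can be exceptionally the same surgeon").

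Section 11.2.3 gives the estimator. "First an unadjusted estimate of the cost-effectiveness ratios will be made", with a bootstrap confidence interval. The next step is "We will then estimate the net monetary benefit of each surgical procedure", and "The distribution of each BNM will be determined by boostrap". The acceptability curve runs over thresholds from €0 to €30,000 "per avoided complication (or Qaly in the secondary criteria"). The 12-month cost per QALY is to be assessed in the same way. The section mentions no covariate, weight or match.

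Adjustment appears in two other places. Section 1.3 says that the hDRS matching and "the statistical methods of adjustment will overcome the absence of randomization" in the assignment to the PUL or TURP cohort. Section 11.2.1 says: "Adjusted comparisons between PUL and the TURP/Laser cohorts and between PUL and SNDS cohorts will be" performed by linear regression for quantitative variables and by logistic regression with confounders for qualitative ones. The data-analysis part of the summary dates these comparisons at 1 year and 3 years.

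**The concern.** In a non-randomised comparison, any patient characteristic that differs between the cohorts and affects complications or costs biases both parts of the ratio. A bootstrap of the unadjusted ratio resamples the same imbalance, so its interval reflects sampling error and shows nothing of this bias. The acceptability curve inherits the problem if no adjustment enters the net benefit.

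Selection is plausible here. Section 1.6 says the device follows the HAS recommendations, and the indication in Appendix 1 includes patients with a contraindication to other endoscopic surgery. Each cohort normally has its own surgeon in a centre (sections 7.1 and 7.2). The results are meant to support a reimbursement decision, so the primary ratio will be read as the effect of the procedure.

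**Working it through.** **1. Does any planned adjustment reach the primary ratio?**

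- *hDRS matching.* Sections 4.1 and 5.2.3 match SNDS patients to PUL patients, 5 to 1 for each transurethral procedure. The TURP/laser cohort, which supplies the comparator for the primary ratio, is not matched.
- *Regression in section 11.2.1.* This names the right pair of cohorts. But it gives no 4-month time point, the summary gives 1 and 3 years, and neither place mentions the ratio or net benefit. For complication yes/no it specifies logistic regression. That yields an odds ratio, and a further step (standardisation to a risk difference) is needed before it can serve as the effect difference in section 11.2.3.
- *Baseline comparison in section 11.2.2.* This flags standardised differences above 10% but attaches no consequence to them. With 80 per cohort the standard error of a standardised difference is about √(2/80) = 0.158. A single covariate would exceed 0.10 by chance alone with probability P(|Z| > 0.10/0.158 = 0.632) ≈ 53%. Flags are therefore likely, and no remedy is stated.

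None of the three produces an adjusted primary result.

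**2. The plan's own precision figures (section 11.1).** The point does not rest on them, but they reproduce. With n = 80, 1.96·√(p(1−p)/80) gives 6.57% at p = 0.10 and 10.96% at p = 0.50 (stated: 7% to 11%). 1.96·CV/√80 gives 13.15% at CV 0.6 and 26.30% at CV 1.2 (stated: 13% to 26%). These are sampling errors only and do not allow for confounding.

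**3. Illustration of what could be at stake.** The protocol gives no inputs for this, so every value is assumed. Let ΔE be complications avoided, with true ΔE = 0.15 and true ΔC = €1,000. The true ratio is 1000/0.15 = €6,667. One binary confounder differs in prevalence between cohorts by d (0.05 to 0.30), raises complication risk by r (0.10 to 0.30) and raises cost by c (€500 to €1,500).

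If it is less common in the PUL cohort: unadjusted ΔE = 0.15 + d·r and unadjusted ΔC = 1000 − d·c.

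- Smallest: (1000 − 25)/(0.15 + 0.005) = 975/0.155 = €6,290
- Largest: (1000 − 450)/(0.15 + 0.09) = 550/0.24 = €2,292

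If it is more common in the PUL cohort, the signs reverse:

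- Smallest: 1025/0.145 = €7,069
- Largest: 1450/0.06 = €24,167

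The true incremental net benefit at a threshold of €30,000 is 30000 × 0.15 − 1000 = €3,500. The error is 30000·d·r + d·c:

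- Smallest: 150 + 25 = €175
- Largest: 2700 + 450 = €3,150

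The sign of the error depends on the direction of the imbalance.

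**4. The 12-month ratio.** If a baseline EQ-5D difference of 0.03 (assumed) persists all year, it adds 0.03 QALY, or 0.03 × 30000 = €900 of net benefit at the top threshold.

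**The case against.** The best defence is that the protocol does not reject adjustment. The word that opens the quoted sentence implies a second step. Section 11.2.1 plans adjusted comparisons of exactly these two cohorts, and cost and complications can be read as falling within them. Covariate lists and model details normally belong in the statistical analysis plan, which sections 11.2.1 and 11.2.4 promise before analysis. Both cohorts share the same eligibility criteria (section 5.1), and section 5.3 tolerates a difference of only 3 cases between groups in a centre.

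Much of this stands. A reader might infer that the protocol has settled on an unadjusted analysis, that it declares the net-benefit curve unadjusted, or that the PUL and TURP/laser cohorts get no adjusted comparison at all. The documents support none of these. Only the ratio is called unadjusted, section 11.2.3 is silent on the net benefit, and section 11.2.1 does plan adjusted comparisons. Nor do the documents show that patients are in fact allocated by indication.

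What does not stand is leaving the matter wholly to the analysis plan. The protocol itself names the estimator of its primary endpoint, names only an unadjusted one, and claims in section 1.3 that adjustment deals with non-randomisation. Shared eligibility and balanced centre counts limit some imbalance, but they do not remove selection within the eligible range or differences between surgeons.

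It is also fair that the bias may be modest beside sampling error. With assumed risks of 30% and 15% and 80 per cohort, the 95% half-width for the risk difference is 1.96·√((0.21 + 0.1275)/80) = 12.7 points. A 3-point bias, for example d = 0.10 and r = 0.30, is about a quarter of that. But such a bias does not shrink with sample size, and no reported interval would show it.

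**Conclusion.** The concern holds as a gap between what section 1.3 promises and what section 11.2.3 specifies. For the primary 4-month result, the protocol fixes only an unadjusted ratio, states no adjustment for the net benefit, and never ties the general regressions to either. Followed as written, the main result carries whatever confounding exists.

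This conclusion rests on the text alone. The illustrative figures (unadjusted ratios from €2,292 to €24,167 around a true €6,667, and net-benefit errors of €175 to €3,150) depend entirely on assumed inputs. A reader might take them as evidence that the ratio will be biased in favour of PUL, or by a known amount. They show neither, because the size and direction are unknown. The gap is smaller for the 12-month QALY ratio, since the summary does place adjusted comparisons at 1 year, but there too nothing links them to the ratio.

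**What to change.** State in section 11.2.3 that the main analysis at 4 months is a confounder-adjusted cost difference, effect difference (as a risk difference) and net benefit. Net-benefit regression or propensity weighting, carried out inside each bootstrap sample, would do this. Prespecify baseline covariates that are already collected: centre, age, IPSS, peak flow, prostate volume and medical history, plus baseline EQ-5D for the 12-month QALY analysis. Keep the unadjusted ratio as descriptive. Align the summary (adding the 4-month time point) and sections 1.3, 11.2.1 and 11.2.3.

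Two further statements are needed:

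- *Hospital cost.* Section 4.2 plans micro-costing of about 30 stays, extended only if they prove heterogeneous, while net-benefit regression needs a cost for each of the 160 patients. The plan should say how the others are costed. One option is to apply unit costs from the observed stays to each patient's own implants, operating time and length of stay, which section 1.3 lists among the information to be gathered. Assigning one mean per cohort would leave nothing in that component for covariates to adjust.
- *Surgeon.* Where each cohort has a different surgeon within a centre, surgeon and procedure cannot be separated. Adjusting for centre does not remove this, and section 1.3 should be softened accordingly.

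The cost is wording and slightly more analysis work, with no new baseline data. The drawback is some model dependence with 160 patients, so the covariate list should be short and fixed before the 4-month data are analysed.

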1.1.2. ON THE STRATEGIES/PROCEDURES AND THE STUDY

1.1.2.1. Transurethral surgery

In France about 60.000 transurethral procedures for BOO are performed each year. However, even if bipolar and laser surgery have dramatically improved surgical outcomes in terms of length of hospital stay and post-operative complications, these procedures remain associated with a significant amount of infectious and bleeding complications, as well as with some persistent side effects such as sexual dysfunction and urinary incontinence (2, 3).

The incidence of post-operative complications has been evaluated in many RCTs comparing different surgical procedures. Clavien Dindo complications grade 2 and higher were experienced by 20 to 40% of patients depending on the surgical technique. Most of complications related with surgery are occurring within 3 months after surgery. After the first 3 months, delayed complications such as urethral strictures, bladder neck sclerosis and urinary incontinence may lead to additional surgical treatments. LUTS recurrence may also lead to restarting medical treatment or secondary surgical treatment .

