11. STATISTICAL ASPECTS

11.1. CALCULATION OF STUDY SIZE

In the SNDS, the study size will depend on the number of patients initially recruited. The expected number of patients will thus be for:

- **PUL Cohort:** 80 patients with PUL;
- TURP/Laser Cohort: 80 patients for the TURP or laser surgery
- **SNDS Cohort:** 1200 patients distributed between 400 matched TURP patients, 400 matched HLE patients and 400 matched HLV patients.

80 patients (in each of the PUL and TURP cohorts) will allow 95% confidence intervals with a precision:

- between 7% and 11% for observed proportions between 10% and 50%
- between 13% and 26% for observed means with coefficient of variation between 0.6 and 1.2.

Furthermore, 80 patients in each PUL and TURP cohorts is largely enough to answer to the primary economic objective (cost-effectiveness ratio, expressed as incremental cost/avoided complications) with a power of 80% and an alpha risk of 5%. In fact, according to the Glick formula¹, the needed number to treat to answer this question is about 40.

400 patients in each of the 3 subgroups of the SNDS cohort will allow 95% confidence intervals with a precision:

- between 3% and 5% for observed proportions between 10% and 50%,
- between 6% and 12% for observed means with coefficient of variation between 0,6 and 1,2.

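### The primary cost-effectiveness ratio gets a bootstrap 95% interval with no provision for a complication difference at or across zero, so at 80 per arm its lower limit can read as a saving when PUL is dearer.

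*Protocol*

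**What the plan says.** Protocol 3.1 defines the endpoint, counting time from surgery: "The primary endpoint will be the incremental cost per avoided complication (based on Clavien Dindo classification) of PUL compared to transurethral surgery 4 months after". Section 11.2.3 writes the ratio as ΔC/ΔE, PUL minus transurethral surgery, with "Eeval = Complications observed at 4 months in the PUL group" and the same definition for the reference group. On uncertainty it states: "Their 95% confidence interval of the ratio will be estimated by bootstrap". It adds that the ratio for cost per QALY at 12 months is assessed in the same way.

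The section does not name the type of bootstrap. It has no rule for replicates in which ΔE is zero or of the opposite sign, and no cost-effectiveness plane. It goes on to bootstrap the net monetary benefit (Eλ − C) of each procedure and to plot the probability that each is highest for λ from €0 to €30,000. No interval is attached to that quantity.

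Section 11.1 fixes 80 patients per cohort and calls this ample for the primary objective, because "the needed number to treat to answer this question is about 40". Section 1.1.2.1 gives the comparator's risk: "Clavien Dindo complications grade 2 and higher were experienced by 20 to 40% of patients depending on the surgical technique". No complication rate for PUL is given.

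**The concern.** A ratio can be ordered only while its denominator keeps one sign. With E as complications avoided, a negative ΔC/ΔE arises in two opposite situations: PUL cheaper and better, or PUL dearer and worse. If replicates are sorted, those in which PUL is dominated fall below every positive ratio and pull the limits towards PUL. A negative lower limit then looks like a possible saving.

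The sign of E as written (complications observed) is a separate matter. Under that convention dearer and worse gives a positive ratio that looks like an ordinary price. Correcting the sign is necessary, but it only moves the ambiguity to negative values.

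The results are meant to support reimbursement (summary, expected impacts; 1.1.2.3), so the reported limits of the primary ratio will be read closely. The 12-month cost per QALY is exposed as well, since 1.3 itself expects EQ-5D to separate the groups poorly. That case was not simulated.

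**Working it through.** **Inputs from the protocol.** 80 per arm and CV of means 0.6–1.2 (11.1); complication rate 20–40% for transurethral surgery (1.1.2.1; this is grade 2 and higher, whereas the primary endpoint fixes no grade); implants about 4 × €500 = €2,000 (1.1.2.3); two-sided 5% (11.2.1).

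**Assumptions.** PUL halves the rate unless stated otherwise; a patient has a complication or not; E is complications avoided; costs are gamma distributed; mean cost is €3,000 for transurethral surgery and €3,000 + ΔC for PUL; the bootstrap uses percentile limits.

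**1. The plan's own precision.** 1.96·√(p(1−p)/80) gives 6.6% at p = 10% and 11.0% at p = 50%. 1.96·CV/√80 gives 13.1% and 26.3%. These reproduce the stated 7–11% and 13–26%. They describe one group, not a difference. The figure of about 40 cannot be reproduced, because its inputs are not given, and nothing below depends on it.

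**2. How often ΔE is not clear of zero.** SE = √(p₁(1−p₁)/80 + p₂(1−p₂)/80). The chance that the 95% interval of the difference reaches zero is about Φ(1.96 − Δ/SE).

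| Transurethral v PUL | SE | Δ/SE | Chance |
|---|---|---|---|
| 20% v 10% | 0.0559 | 1.79 | 57% |
| 30% v 15% | 0.0650 | 2.31 | 36% |
| 40% v 20% | 0.0707 | 2.83 | 19% |
| 30% v 20% | 0.0680 | 1.47 | 69% |
| 30% v 10% | 0.0612 | 3.27 | 10% |

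Simulation (1,000 bootstrap replicates per trial, at least 500 trials per scenario, repeated) agrees. For rates halved from 20%, 30% and 40%, at least 2.5% of replicates have ΔE ≤ 0 in about 57–62%, 36–44% and 18–24% of trials: roughly 20–60%.

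**3. What a negative replicate means at ΔC = €2,000.** At CV 0.6 the cost SDs are €3,000 (PUL) and €1,800. SE(ΔC) = √((3,000² + 1,800²)/80) = €391, so ΔC lies about 5 SE above zero. Practically every negative ratio is therefore dearer and worse.

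**4. Lower limit.** At ΔC = €2,000 and CV 0.6, it is negative although PUL is clearly dearer in about 50–56%, 32–35% and 14–20% of trials (rates halved from 20%, 30%, 40%): about 15–55% overall.

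**5. One worked data set.** Observed 30% v 20%, PUL €2,000 dearer, CV 0.6, base cost €2,253 (the hospital income in 1.1.2.3, as a proxy), 20,000 replicates. The ratio is 2,000/0.10 = €20,000. The percentile limits are −€86,401 and €143,625. PUL is dearer and worse in 5.9% of replicates and cheaper in none, so the negative limit comes entirely from replicates in which PUL is dominated.

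**6. PUL truly dearer and worse** (30% with PUL v 20%, ΔC = €2,000). The whole interval lies below zero in about 20–34% of trials. The net-benefit interval at λ = €30,000 favours PUL in 0%.

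**7. Upper limit.** This compares how often it falls below €30,000 with how often the net-benefit interval at λ = €30,000 favours PUL. At ΔC = €2,000 and CV 0.6 one run gave 9.3% v 9.1%, 27.1% v 26.1% and 49.1% v 47.9%; across runs the gap is about 0–2 points. At an assumed ΔC of €500 it is about 8–24 points, depending largely on whether replicates with ΔE = 0 are set to infinity or dropped.

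**8. Large effects.** For observed 30% v 10%, only 0.07% of replicates have ΔE ≤ 0. With ΔC = €2,000 and CV 0.6 the limits are €5,564 and €25,358, and the interval behaves.

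**The case against.** The sentence in 11.2.3 says only that a bootstrap is used. Percentile sorting is assumed here, and the type of bootstrap may properly be left to the SAP; an ordered bootstrap would satisfy the same sentence. That stands, and the frequencies above are conditional on percentile limits. It does not dispose of the point. The protocol itself chooses the ratio as the quantity that receives the interval, without condition, and naming another simple bootstrap type does not stop two opposite quadrants sharing a sign.

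The net monetary benefit is already bootstrapped in the same section, and its acceptability curve would expose a dominated PUL. That stands too, once the sign of E is corrected: as written, Eλ − C rewards complications. The defect therefore lies in the reported ratio interval and not in the analysis as a whole.

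Two stronger readings are tempting. A reader might infer that PUL would be declared cost-effective wrongly because the upper limit falls below €30,000. The protocol contains no such rule: €30,000 is only the end of the λ range, and at the implant-based increment of €2,000 the upper limit is hardly affected. The larger gap needs ΔC = €500, which is not in the documents. A reader might also infer that the interval will usually mislead. That depends on the PUL complication rate, which is not given.

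**Conclusion.** The point holds as a should-fix. The protocol commits the primary ratio to an interval whose limits lose their meaning when ΔE is not clear of zero. At 80 per arm, with comparator rates of 20–40% and an assumed halving, that happens in roughly 20–60% of trials. The main harm is a negative lower limit that looks like a saving, in about 15–55% of trials when PUL is about €2,000 dearer. If PUL is in truth dearer and worse (30% v 20%), the whole interval falls below zero in about 20–34%. These figures rest on the assumed PUL rate, base cost of €3,000, cost distribution and CV (0.6 for the 15–55%), and on percentile limits. The documents do not support a claim of wrong decisions through the upper limit, or of a flaw that the planned acceptability curve could not reveal.

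**What to change.** In 11.2.3:

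- Define E as complications avoided, in both the ratio and the net monetary benefit.
- Make the bootstrap 95% interval of the incremental net monetary benefit, λΔE − ΔC, over λ from €0 to €30,000 the inferential result, at 4 months and, with QALYs, at 12 months.
- Report the ratio as a point estimate, with separate intervals for ΔC and ΔE, the cost-effectiveness plane and the share of replicates in each quadrant.
- Give an interval for the ratio (Fieller or ordered bootstrap) only when the interval for ΔE excludes zero.

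The cost is wording only, because the planned bootstrap already supplies the replicates. The downside is that many likely results would carry no single interval for the ratio.
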